Please note: This eligibility criteria is also applicable for patients enrolled for the preliminary expansion cohort to conduct preliminary efficacy analysis.

NOTE: Tissue or blood cell free DNA are allowed for genomic profiling of tumor. Profiling should have been performed at a CLIA certified lab ≤1 year prior to registration.

NOTE: Patients in the dose escalation phase are not required to have such mutations. Although genomic profiling is not required for dose escalation patients, it is encouraged in these patients prior to or after study registration if feasible.

3.1.7 Patients must be age ≥ 18 years; both male and females are eligible.

3.1.8 Patients must exhibit an ECOG performance status of ≤2.

3.1.9 Patients must have adequate organ and bone marrow function ≤ 14 days prior to registration, as defined below (Note: Blood transfusion or growth factors is not permitted within 14 days of registration):

absolute neutrophil count	≥ 1.5 x 10 ⁹ /L
hemoglobin	≥ 9 g/dL
platelets	≥ 100 x 10(9)/L
Total bilirubin	≤ 1.5 x ULN
Alanine amino transferase and aspartate aminotransferase	≤ 5 x ULN
Calculated creatinine clearance according to the Cockcroft and Gault equation	≥ 50 mL/min

3.1.10 Females of child-bearing potential (FOCBP) and men who are sexually active with FOCBP must agree to follow instructions for method(s) of contraception for the duration of treatment and the designated post-treatment period (5 months for females and 7 months for males; see Appendix A for details on appropriate contraception methods)

NOTE: A FOCBP is any woman (regardless of sexual orientation, having undergone a tubal ligation, or remaining celibate by choice) who meets the following criteria:

- Has not undergone a hysterectomy or bilateral oophorectomy
- Has had menses at any time in the preceding 12 consecutive months (and therefore has not been naturally postmenopausal for > 12 months)

3.1.11 FOCBP must have a negative pregnancy test ≤ 7 days prior to registration.

3.1.12 Patients must be able to swallow oral medication.

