Grade 3 or 4	Permanently discontinue study drug/study regimen	
 • Discuss with study physician • Monitor stool frequency and volume and maintain hydration • Urgent GI consult and imaging as appropriate • Initiate empiric IV corticosteroids (e.g., methylprednisolone IV or equivalent) at 1 to 2 mg/kg/day • If no improvement within 3-5 days, consider further immunosuppressives (e.g., infliximab). • Caution: Ensure GI consult to rule out bowel perforation and refer to label before using infliximab. Once improving, gradually taper steroids over ≥4 weeks and consider prophylactic antibiotics

Hepatitis (Elevated LFTs)		
*See section for 7.2.5 for a description of AESI's, defined as any increase in ALT or AST to greater than 3 × ULN and concurrent increase in bilirubin to greater than 2 × ULN. Such AESI's should be monitored carefully and discussed with the treating physician (PI or sub-I) to determine attribution.		
Grade	Dose Modifications	Toxicity Management
Any Grade		
 Monitor and evaluate liver function test: AST, ALT, ALP and total bilirubin Evaluate for alternative etiologies (e.g., viral hepatitis, disease progression, concomitant medications)
Grade 1	Continue dosing. If it worsens, treat as Grade 2 event	
 Continue LFT monitoring per protocol
Grade 2*	Hold Study drug up to 28 days until resolution to ≤ Grade 1 or baseline 
 If toxicity worsens then treat as Grade 3 or Grade 4 If improves then treat at next scheduled treatment date 	
 Discuss with study physician if no resolution to ≤ Grade 1 in 1-2 days Recheck LFT's in 1 to 2 days. If event is persistent (> 3-5 days) or worsens, consider prednisone 0.5 to 1 mg/kg/day or IV equivalent. If no improvement within 3-5 days, consider additional workup and treatment with IV methylprednisolone 2-4mg/kg/day 
 If no improvement within 3-5 days after methylprednisolone, consider further immunosuppressives (e.g., mycophenolate mofetil) Once improving, gradually taper steroids over ≥4 weeks and consider prophylactic antibiotics

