Grade 3 or higher	For elevations in transaminases ≥ 5 × ULN, or elevations in bilirubin ≥ 3 × ULN, permanently discontinue study drug/study regimen.	
 Discuss with the study physician Initiate empiric IV corticosteroids (e.g., methylprednisolone IV or equivalent) at 1 to 4 mg/kg/day 
 If no improvement within 3-5 days, consider further immunosuppressive therapy (e.g., mycophenolate mofetil) If still no further improvement within 3-5 days consider other immunosuppressive therapy per local guidelines Hepatology consult, abdominal workup, and imaging as appropriate. Once improving, gradually taper steroids over ≥4 weeks and consider prophylactic antibiotics
Immune-Mediated Nephritis and Renal Dysfunction		
Any Grade		
 Monitor and evaluate renal function tests (comprehensive chemistry panel) Evaluate for alternative etiologies
Grade 1	Continue dosing.	
 Continue comprehensive chemistry plan per protocol
Grade 2 or 3	Hold Study drug up to 28 days until resolution to ≤ Grade 1 or baseline 
 If toxicity worsens then treat as Grade 	
 Discuss with the study physician Consider empiric steroids at a dose of 0.5 to 1 mg/kg/day or IV equivalent. Consider renal biopsy with nephrology consult

	
3 or Grade 4
 
 If improves to baseline then treat at next scheduled treatment date 	
 Monitor creatinine every 2-3 days
Grade 4	Permanently discontinue study drug/study regimen	
 Discuss with the study physician Nephrology consult Monitor creatinine daily Administer corticosteroids at a dose of 1-2 mg/kg/day prednisone equivalents followed by corticosteroid taper for life-threatening (Grade 4) serum creatinine elevation and permanently discontinue. For severe (Grade 3) withhold and administer corticosteroids at a dose of 0.5 to 1 mg/kg/day prednisone equivalents followed by corticosteroid taper. If worsening or no improvement occurs, increase dose of corticosteroids to 1 to 2 mg/kg/day prednisone equivalents and permanently discontinue.
Rash (excluding Bullous skin formations)		
Grade	Dose Modifications	Toxicity Management
Any Grade		Monitor for signs and symptoms of dermatitis (rash and pruritus) **IF THERE IS ANY BULLOUS FORMATION, THE STUDY PHYSICIAN SHOULD BE CONTACTED**

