7.2.5 Adverse Event of Special Interest (AESI)

An AESI is one of scientific and medical interest specific to understanding of the investigational product and may require close monitoring. An AESI may be serious or non-serious. The close monitoring and discussion of AESIs allows ongoing surveillance of these events in order to characterize and understand them in association with the use of this investigational product. The following are considered to be AESI:

- **Hepatic Function Abnormality**
Hepatic function abnormality is defined as any increase in ALT or AST to greater than 3 × ULN and concurrent increase in bilirubin to greater than 2 × ULN. Concurrent findings are those that derive from a single blood draw or from separate blood draws taken within 8 days of each other. Follow-up investigations and inquiries will be initiated promptly by the investigational site to determine whether the findings are reproducible and/or whether there is objective evidence that clearly supports causation by a disease (e.g., cholelithiasis and bile duct obstruction with distended gallbladder) or an agent other than the investigational product.

If the underlying diagnosis for the hepatic function abnormality is known (including progression of pre-existing disease such as primary or metastatic malignancy), the diagnosis should be recorded as an AE/SAE.

If the underlying diagnosis for the hepatic function abnormality remains unknown, the term "hepatic function abnormal" should be used to report the

AE/SAE. Hepatic function abnormality of unknown etiology, or which is considered attributable to investigational product, is required to be reported as “hepatic function abnormal”. The investigator will review the data with the PI. The investigator should then use clinical judgment to establish the cause based on local standard of care and follow the subject by conducting testing as clinically indicated.

- **Pneumonitis**

Adverse events of pneumonitis are also of interest, as pneumonitis has been observed with anti-PD-1 and anti-PD-L1 mAbs. Initial work-up should include high-resolution CT scan, ruling out infection, and pulse oximetry. Pulmonary consultation is highly recommended.

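### The ALT/AST entry limit meets the Table 4.6 permanent-stop level at 5 x ULN, that stopping row has no baseline or repeat-value condition, and the Appendix D hepatic footnote gives a different instruction for the same values

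*Combined protocol and SAP*

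**What the plan says.** **Entry.** Section 3.1.9 sets one transaminase limit for all patients, "Alanine amino transferase and aspartate aminotransferase ≤ 5 x ULN", and a bilirubin limit, "Total bilirubin ≤ 1.5 x ULN".

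**Stopping.** Section 4.5.2, Table 4.6, hepatitis, Grade 3 or higher: "For elevations in transaminases ≥ 5 × ULN, or elevations in bilirubin ≥ 3 × ULN, permanently discontinue study drug/study regimen". The row names no baseline and no confirmatory value.

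**The row above it.** The Grade 2 hepatitis row does refer to baseline, "Hold Study drug up to 28 days until resolution to ≤ Grade 1 or baseline", and does ask for a repeat, "Recheck LFT's in 1 to 2 days".

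**Appendix D.** The footnote to the hepatic algorithm lets immuno-oncology therapy be delayed instead of discontinued when AST/ALT is at or below 8 x ULN or total bilirubin is at or below 5 x ULN.

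**Attribution.** Section 4.4 requires no modification for events clearly not due to the study drugs or for laboratory abnormalities that are not clinically significant. Where attribution is uncertain, it sends both drugs to the same guidelines. The overall-management part of Table 4.6 adds that events without a clear alternative cause are to be considered potentially immune related.

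**The concern.** An entry limit and a permanent-stop limit normally have a margin between them, or the stop is expressed relative to the patient's baseline. Here the two limits touch, and the irreversible action is the one hepatitis action that depends on a fixed multiple alone. A patient with liver metastases or another stable reason for raised enzymes could enter at 4.5 x ULN, drift to 5.1 x ULN, and fall within the row.

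Section 4.4 helps if the investigator judges the change clearly unrelated or not clinically significant. A small rise over an already raised baseline during checkpoint inhibition is often neither, and the uncertain case returns to Table 4.6. The investigator then finds that Appendix D permits a delay for the same value.

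The statistical stake is exposure in a very small analysis set. The success rule uses 10 patients with mutations and response at the first scan, at 8 weeks (sections 1.9, 4.3.3, 10.2). Replacement is allowed only before C1D1 (section 4.10), so a patient stopped after that stays in the denominator, and each is 1/10 of the analysis. Inconsistent handling of the same value would also make the discontinuation data hard to interpret.

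**Working it through.** The plan states no figure on this point, so there is nothing to reproduce. The check is a side-by-side reading followed by an illustration.

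**Step 1: one value against each passage.**

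| ALT or AST | 3.1.9 | Table 4.6, Grade 3 or higher row | Appendix D footnote |
|---|---|---|---|
| 4.9 x ULN | eligible | below the row's limit | within the delay range |
| 5.0 x ULN | eligible | permanent stop | within the delay range |
| 5.1 to 8.0 x ULN | not eligible | permanent stop | within the delay range |
| above 8.0 x ULN | not eligible | permanent stop | outside the delay range |

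The second line shows the overlap with eligibility. The second and third lines show the conflict between Table 4.6 and Appendix D. The same conflict exists for bilirubin from 3 to 5 x ULN. The algorithm figure is not in the text available to us, so the step to which the footnote attaches cannot be seen, but its words cover these values.

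**Step 2: how often could variation alone reach 5 x ULN?**

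Inputs:
- Threshold: 5 x ULN (Table 4.6).
- Draws: C1D8, C1D15, C2D1 and C2D15, from the chemistry row of Table 5. Induction Day 1 and C1D1 are left out because they precede any nivolumab and Table 4.6 concerns nivolumab-related toxicity. C3D1 is left out because the first scan is due then or in the 7 days before.
- Within-patient CV: not in the documents. Assumed 10–20%, with 30% as a sensitivity case.
- Draws independent around a constant usual level m, one transaminase modelled, no drug effect: all assumptions.

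Formulas: s = √ln(1 + CV²), so s = 0.0998, 0.198 and 0.294 for CV 10%, 20% and 30%. Single draw: p = 1 − Φ(ln(5/m)/s). At least one of four: P = 1 − (1 − p)⁴.

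Example, m = 4.0 and CV 20%: ln(1.25)/0.198 = 1.127, p = 0.1299, P = 1 − 0.8701⁴ = 0.427.

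| Usual level | p, CV 10% | P | p, CV 20% | P | p, CV 30% | P |
|---|---|---|---|---|---|---|
| 3.0 x ULN | 0.0000 | 0% | 0.0049 | 2% | 0.0409 | 15% |
| 3.5 x ULN | 0.0002 | 0.1% | 0.0359 | 14% | 0.1122 | 38% |
| 4.0 x ULN | 0.0126 | 5% | 0.1299 | 43% | 0.2236 | 64% |
| 4.5 x ULN | 0.1454 | 47% | 0.2974 | 76% | 0.3598 | 83% |

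**Step 3: the same model at the Appendix D level.** For m = 4.5 and CV 20%, the chance of exceeding 8 x ULN is p = 1 − Φ(ln(8/4.5)/0.198) = 0.0018 per draw, and 1 − (1 − 0.0018)⁴ ≈ 0.7% over four draws. For this patient, the choice of passage changes the chance of a result beyond the relevant limit from 76% to under 1%.

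These are probabilities that a value reaches a limit. They equal probabilities of being stopped only if every such value is judged attributable, or uncertain, and clinically significant.

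**The case against.** The strongest reply is that the protocol has many safeguards and the overlap is a boundary matter in one row. Much of this stands.

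- A reader might infer that the plan has no baseline or repeat-value rule at all. It does. The Grade 2 hepatitis row has both, section 4.5.1 lets veliparib toxicity recover to baseline where Grade 2 was present at entry, and section 7.2.1 says that a preexisting condition that does not worsen is not an adverse event. The gap is confined to the Grade 3 or higher row.
- A reader might infer that the MTD is compromised. Section 4.3.1 requires a non-hematologic DLT to be at least a 2-grade increase from baseline, so it is protected.
- A reader might infer that patients entering above 3 x ULN already meet the hepatic event of special interest. Section 7.2.5 requires "any increase in ALT or AST to greater than 3 × ULN and concurrent increase in bilirubin to greater than 2 × ULN". Entry caps bilirubin at 1.5 x ULN, so no eligible ALT/AST value meets the definition alone, and the section also asks sites "to determine whether the findings are reproducible". Section 10.3 plans no separate count of these events.
- Section 4.4 exempts abnormalities that are not clinically significant, so not every value of 5 x ULN or more leads to a stop.
- Appendix D offers a way out. But it does so by contradicting Table 4.6, which is the reason to reconcile the two.

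Four of the 10 patients had already been treated at the MTD when the plan was modified, so the effect on the success analysis concerns at most the six new patients and cannot be quantified from the documents.

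**Conclusion.** The point holds in a limited form. The current text makes 5.0 x ULN both an eligible value and a permanent-stop value, gives no baseline or repeat condition in that row, and contradicts itself between Table 4.6 and Appendix D. These facts need no assumptions.

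The size does need them. With a CV of 10–20% and four independent draws, the chance of at least one value at the stopping level without drug effect is 0–14% at a usual level of 3.5 x ULN, 5–43% at 4.0 and 47–76% at 4.5. It is about 2% or less at 3.0 or below, rising to 15% at 3.0 if the CV is 30%. The problem therefore matters for patients who enter at about 4 to 5 x ULN. Their share is not given; if none enter there, the practical effect is small.

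The documents do not support wider claims that the MTD, the special-interest definition or the adverse-event counts are generally distorted.

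**What to change.** Reconcile three passages: section 3.1.9, the Grade 3 or higher hepatitis row of Table 4.6, and the Appendix D hepatic footnote. State how they apply to a patient whose ALT/AST is already raised at entry, and which passage governs where Table 4.6 and Appendix D differ. Which limit applies is a clinical decision for the investigators, and none is proposed here.

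Optionally, add to section 10.3 a table of hepatic laboratory results as a shift from baseline grade. This is descriptive: it lets a reader see which high values came from raised baselines, but it does not remove variation near a grade boundary, since a move from 4.9 to 5.1 x ULN would still appear as a shift.

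The cost is a short amendment and, if wanted, one table. Screening and on-treatment chemistry are already collected under Table 5, so no new data are needed.

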*See section 7.2.5 for a description of AESI's (Adverse Events of Special Interest). Such AESI's should be monitored carefully and discussed with the treating physician (PI or sub-I) to determine attribution.		
Grade	Dose Modifications	Toxicity Management
Any Grade		
 Monitor subjects for signs and symptoms of pneumonitis or ILD (new onset or worsening shortness of breath or cough). Subjects should be evaluated with imaging and pulmonary function tests including other diagnostic procedures as described below Initial work-up may include clinical evaluation, monitoring of oxygenation via pulse oximetry (resting and exertion), laboratory work-up and high-resolution CT scan.
Grade 1	No dose hold required. However, consider holding study drug/study regimen dosing as clinically appropriate and during diagnostic work-up for other etiologies.	
For Grade 1 (Radiographic Changes Only)
 
 Monitor and closely follow up in 2-3 days for clinical symptoms, pulse oximetry (resting and exertion) and laboratory work- up and then as clinically indicated Consider pulmonary and infectious disease consult Re-image at least every 3 weeks
Grade 2	
Hold study drug up to 28 days until resolution to ≤ Grade 1 or baseline:
 
 If toxicity worsens then treat as Grade 3 or Grade 4 If toxicity improves then treat at next scheduled treatment date 	
For Grade 2 (Mild to Moderate New Symptoms)
 
 Monitor symptoms daily and consider hospitalization Discuss with study physician and consider systemic steroids (e.g., prednisone 1- 2mg/kg/day or IV equivalent) Reimaging as clinically indicated If no improvement within 3-5 days, additional workup and treatment with IV methylprednisolone 1mg/kg/day should be considered If no improvement within 3-5 days, further immunosuppressive therapy (e.g., infliximab) should be considered. Once improving, gradually taper steroids over ≥4 weeks and consider prophylactic antibiotics Consider pulmonary and infectious disease consult
Grade 3 or 4	Permanently discontinue study drug/study regimen	
For Grade 3 or 4 (severe or new symptoms, new/worsening hypoxia, life threatening)
 
 Discuss with study physician pulmonary and infectious disease consult

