Any Grade		
 Monitor subjects for signs and symptoms of endocrinopathies. Non-specific symptoms include headache, fatigue, behavior changes, changed mental status, vertigo, abdominal pain, unusual bowel habits, hypotension and weakness. Subjects should be thoroughly evaluated to rule out any alternative etiology (e.g., disease progression including brain metastases, infections, etc.) Monitor and evaluate thyroid function tests: TSH, free T₃ and free T₄ and other relevant endocrine labs depending on suspected endocrinopathy. If a subject experiences an AE that is thought to be possibly of autoimmune nature (e.g., thyroiditis, pancreatitis, hypophysitis, diabetes insipidus), the investigator should send a blood sample for appropriate autoimmune antibody testing
Grade 1	Continue dosing.	For Grade 1: (including those with asymptomatic TSH elevation) 
 Monitor patient with appropriate endocrine function tests If TSH < 0.5X LLN, or TSH >2X ULN or consistently out of range in 2 subsequent measurements, include FT4 at subsequent cycles as clinically indicated and consider endocrinology consult.
Grade 2	Hold study drug up to 28 days until resolution to ≤ Grade 1 
 If worsens then treat as Grade 3 or Grade 4 If toxicity improves to baseline then treat at next scheduled treatment date 	For Grade 2: (including those with symptomatic endocrinopathy) 
 Discuss with study physician Initiate hormone replacement as needed for management Evaluate endocrine function, and as clinically indicated, consider pituitary scan For subjects with abnormal endocrine work up, consider short-term, high-dose corticosteroids (e.g., methylprednisolone or IV equivalent) with relevant hormone replacement (e.g., levothyroxine, hydrocortisone, or sex hormones) For subjects with normal endocrine work up (lab or MRI scans), repeat labs/MRI as clinically indicated.

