Grade 3	Hold study drug up to 28 days until endocrinopathy symptom(s) are controlled. Resume study drug/study regimen administration if controlled at the next scheduled dose.	
 Discuss with study physician Initiate empiric IV corticosteroids (e.g., methylprednisolone IV or equivalent) at 1 to 2 mg/kg/day Administer hormone replacement therapy as necessary For adrenal crisis, severe dehydration, hypotension, or shock: immediately initiate intravenous corticosteroids with mineralocorticoid activity Consult endocrinologist Once improving, gradually taper immunosuppressive steroids over ≥4 weeks
Grade 4	Permanently discontinue study drug/study regimen	
Immune mediated Neurotoxicity (except Myasthenia Gravis and Guillain-Barre)		
Grade	Dose Modifications	Toxicity Management
Any Grade		
 Subjects should be evaluated to rule out any alternative etiology (e.g., disease progression, infections, metabolic syndromes and

		
medications, etc.)
 
 • Monitor subject for general symptoms (headache, nausea, vertigo, behavior change, or weakness) • Consider appropriate diagnostic testing (e.g. electromyogram and nerve conduction investigations) • Symptomatic treatment with neurological consult as appropriate
Grade 1	Continue dosing	
Grade 2	
 • For acute motor neuropathies or neurotoxicity, hold study drug up to 28 days until resolution to ≤ Grade 1 • For sensory neuropathy/neuropathic pain, consider holding study drug up to 28 days until resolution to ≤ Grade 1 or baseline. 
 ○ If toxicity worsens then treat as Grade 3 or Grade 4 ○ If toxicity improves then treat at next scheduled treatment date 	
 • Discuss with the study physician • Consider Neurology Consult • Sensory neuropathy/neuropathic pain may be managed by appropriate medications (e.g., gabapentin, duloxetine, etc.) • Consider systemic steroids prednisone 1- 2mg/kg/day or IV equivalent at 0.5 to 1 mg/kg/day • If no improvement within 3-5 days, consider additional workup and treatment with additional immunosuppressive therapy (e.g. IVIgG)

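### Table 4.6 names two restart thresholds within single cells for endocrinopathy and nephritis, and puts Grade 3 nephritis instructions in two rows

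*Combined protocol and SAP*

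**What the plan says.** Section 4.4 of the protocol says that nivolumab doses cannot be modified but can be delayed or discontinued as Table 4.6 directs, and that missed doses are skipped. Table 4.6 (Section 4.5.2) then gives these rules.

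- Endocrinopathy, Grade 2. Hold line: "Hold study drug up to 28 days until resolution to ≤ Grade 1". Restart line in the same cell: "If toxicity improves to baseline then treat at next scheduled treatment date".
- Endocrinopathy, Grade 3. Hold line: "Hold study drug up to 28 days until endocrinopathy symptom(s) are controlled". Restart line: "Resume study drug/study regimen administration if controlled at the next scheduled dose".
- Nephritis, Grade 2 or 3. Hold line: "Hold Study drug up to 28 days until resolution to ≤ Grade 1 or baseline". Restart line in the same cell: "If improves to baseline then treat at next scheduled treatment date". The management column says that steroids should be considered.
- Nephritis, Grade 4. The management cell also carries a Grade 3 instruction: withhold drug and give corticosteroids, then "If worsening or no improvement occurs, increase dose of corticosteroids to 1 to 2 mg/kg/day prednisone equivalents and permanently discontinue".

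Elsewhere in the table, the Grade 2 cells with a restart line (immune-related events overall, pneumonitis, diarrhea, hepatitis, rash, neurotoxicity) ask only for improvement, for example "If toxicity improves then treat at next scheduled treatment date". A return to baseline appears as the restart condition only in the endocrinopathy Grade 2 and nephritis Grade 2 or 3 cells.

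Section 4.3.1 sets a further rule. When a toxicity meets the DLT criteria, the combination is interrupted until the event is at Grade 1 or lower, or at baseline.

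**The concern.** A hold rule should say at what point dosing resumes. In two cells the line that ends the hold and the line that resumes treatment name different points, and a patient can lie between them. For Grade 3 nephritis, whether a patient without improvement stays on hold or is taken off nivolumab depends on which row the investigator reads. For Grade 3 endocrinopathy that is a DLT, two sections state the restart condition in different terms.

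These are operative rules on re-exposure after an immune-related toxicity, so they bear on patient safety first. They also affect the data: nivolumab exposure and any count of delays or discontinuations would reflect the line each investigator followed as well as the drug's tolerability. Section 4.4 lists endocrinopathies among the immune-related events that may be seen, and Section 8.2.10 names renal and endocrine events among the groups that have management algorithms. The documents give no rate for either.

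**Working it through.** The plan has no figure to reproduce here. The check sets the clauses side by side.

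**Step 1: the two lines within each cell.** Let b be the baseline grade and c the current grade. Read improvement to baseline as c ≤ b.

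- Endocrinopathy Grade 2: the hold ends if c ≤ 1; the treat line is met if c ≤ b.
- Nephritis Grade 2 or 3: the hold ends if c ≤ 1 or c ≤ b; the treat line is met if c ≤ b.

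| b | c | Hold line met (either cell) | Treat line met | Lines agree |
|---|---|---|---|---|
| 0 | 0 | yes | yes | yes |
| 0 | 1 | yes | no | **no** |
| 1 | 0 or 1 | yes | yes | yes |

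Both cells fail at the same place: a Grade 0 baseline with the event settling at Grade 1. A Grade 2 baseline would reverse the endocrinopathy mismatch at c = 2. Section 3.2.14 admits hypothyroidism on stable replacement but does not give its grade, so I do not rely on that case. In nephritis it cannot arise, because the hold line includes baseline.

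**Step 2: Grade 3 nephritis in two rows.**

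| | Grade 2 or 3 row | Grade 3 text in the Grade 4 cell |
|---|---|---|
| Drug | hold up to 28 days | withhold, no time limit stated |
| Steroids, 0.5 to 1 mg/kg/day | to be considered | to be given |
| Worsening | treat as Grade 3 or 4 | raise steroids, discontinue permanently |
| No improvement | no separate rule | raise steroids, discontinue permanently |

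The steroid range is the same in both. They differ on whether steroids are given or considered, on worsening that stays within Grade 3, and on lack of improvement.

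**Step 3: Grade 3 endocrinopathy against the DLT rule.** A Grade 3 endocrinopathy that is at least two grades above baseline and falls in the 28-day window can be a DLT (Section 4.3.1, item 1). Table 4.6 then resumes once symptoms are controlled, and Section 4.3.1 resumes at c ≤ 1 or c ≤ b. Suppose, as an assumption, that symptoms are judged controlled while the event is still Grade 2 from a Grade 0 baseline. The table line is met and the Section 4.3.1 line is not. The documents do not define control by grade, so how often this would occur cannot be worked out.

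**Step 4: size.**

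- Scheduled nivolumab doses spanned by a full 28-day hold: 28 / 14 = 2 doses of 240 mg in Cycles 1-4; 28 / 28 = 1 dose of 480 mg from Cycle 5.
- Doses scheduled before the first scan at 8 weeks: 56 / 14 = 4. One skipped dose is 1/4 = 25% of planned nivolumab before that scan.
- Patients at the MTD: 6 treated + 6 planned = 12 (Section 10.2). If a discontinuation proportion is reported, one patient classified differently moves it by 1/12 = 8.3 percentage points.
- The success rule stays at three or more responses in 4 + 6 = 10 patients with a mutation.

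**The case against.** The strongest reply is that this is loose drafting and not a pair of opposite orders. The baseline lines begin with if, not only if. Return to baseline can be read as one sufficient reason to treat, and no line forbids restart at Grade 1. The table's overall Grade 2 row holds to Grade 1 or baseline and then treats on improvement, which gives a rule to read the two cells against. Section 4.4 also describes Tables 4.5 and 4.6 as general guidelines, and the rows at issue ask for discussion with the study physician. This stands in part: the text does not order that a patient be restarted and kept off at once. But it does not say which line governs, and the wording that departs from the other Grade 2 cells is confined to these two.

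On nephritis, one can say that the Grade 3 text is merely misplaced, since worsening to Grade 4 already leads to permanent discontinuation. That is fair for worsening to Grade 4. It does not cover a Grade 3 event that fails to improve.

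The Appendix D algorithms and the Investigator's Brochure might settle the point. The figures are not shown and the brochure is not included, so this cannot be checked and is not counted against the plan. The table's own lines would still differ.

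A reader might also infer that the restart rule is stricter after Grade 2 than after Grade 3 endocrinopathy, so that a patient stable on hormone replacement could restart after the worse event but not after the milder one, or has no restart at all under the Grade 2 row. The documents do not support this. The Grade 2 hold ends at Grade 1 or lower, and the adjacent cell uses hormone replacement as management. Nothing says that a patient controlled on replacement stays above that threshold; the grading definitions are only linked, in Appendix B. Control is not defined by grade, no patient is under both rows at once, and Section 4.3.1 adds a grade condition when the Grade 3 event is a DLT.

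**Conclusion.** The point holds as an internal inconsistency in operative rules, not as a fault of design. It has three parts:

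- two cells with mismatched hold and treat lines, which diverge for a Grade 0 baseline settling at Grade 1;
- Grade 3 nephritis instructed in two rows that differ on steroids and on lack of improvement;
- a Grade 3 endocrinopathy restart condition that names no grade and differs from Section 4.3.1 when the event is a DLT.

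The first part rests on reading the treat line as the condition for restart, which is natural but not explicit. The third matters only if symptoms can be judged controlled above Grade 1 and above baseline.

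The consequence is bounded. It concerns individual patients' re-exposure and the descriptive record of exposure and discontinuation. The number affected cannot be estimated from the documents. The MTD is already declared, and the sample size and the response-rate success rule do not change. The change should still be made, because re-exposure rules after immune-related toxicity ought to read one way.

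**What to change.** In an amendment, reconcile four places: the Grade 2 and Grade 3 endocrinopathy cells, the Grade 2 or 3 nephritis cell, the Grade 3 text inside the Grade 4 nephritis cell, and the DLT interruption rule in Section 4.3.1.

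- Make the hold line and the restart line of each cell name the same threshold, so that each event and grade has one.
- Put all Grade 3 nephritis instructions in one row, including what follows if there is no improvement.
- State what controlled means for Grade 3 endocrinopathy, and say whether the table or Section 4.3.1 governs when the event is a DLT.
- Check the result against the Appendix D algorithms.

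The sponsor and investigators decide which thresholds apply; this review takes no view on that. The cost is table and section wording plus the usual amendment approvals (Section 11.2). No new data, visits or recalculation are needed.
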